6.2.16. Skin Inspection

Study staff will inspect the skin on the subject's abdomen during screening and subsequent in-clinic visits. Any anomalies will be recorded. Subjects and their caregivers will also be instructed to monitor for any skin reactions after dosing.

7. ADVERSE EVENTS

The Investigator is responsible for the detection and documentation of events meeting the definition of an adverse event (AE) or serious adverse event (SAE) as provided in this protocol. AEs will be assessed continuously through the last study visit unless the nature of the AE or SAE requires continued monitoring. All AEs are recorded as mild, moderate or severe, and as Not Related, Possibly Related, Probably Related, and Definitely Related to the investigational product.

7.1. Definition of an Adverse Event

An AE is any untoward medical occurrence associated with the use of an investigational product in humans, whether or not considered related to the investigational product. An adverse event (also referred to as an adverse experience) can therefore be any unfavorable and unintended sign (including an abnormal laboratory finding), symptom, or disease temporally associated with the use of an investigational product, and does not imply any judgment about causality. An adverse event can arise with any use of the investigational product (e.g., off-label use, use in combination with another drug) and with any route of administration, formulation, or dose, including an overdose.

A “pre-existing” condition is one that is present prior to administration of the investigational product and is reported as part of the Subject’s medical history. Pre-existing conditions should be reported as AEs only if the frequency, intensity, or character of the pre-existing condition worsens during the course of the study.

Laboratory or functional test abnormalities generally are not considered AEs unless they are associated with clinical signs or symptoms or require medical intervention. A laboratory abnormality (e.g. a clinically significant change detected on clinical chemistry, hematology, urinalysis) or functional test abnormality (e.g. a clinically significant change detected on electrocardiogram, pulse oximetry, or spirometry) that is independent from a known underlying medical condition and that requires medical or surgical intervention, or leads to interruption or discontinuation of the investigational product, must be considered an AE.

All AEs judged to be clinically significant, including clinically-significant laboratory, electrocardiogram and functional test abnormalities, will be followed until resolution or return to baseline or until no further improvement is expected.

An AE does include any:

- Exacerbation of a pre-existing illness.
- Increase in frequency or intensity of a pre-existing episodic event or condition.
- Condition detected or diagnosed after investigational product placement and/or drug administration even though it may have been present prior to the start of the study.
- Continuous persistent disease or symptoms present at baseline that worsen following the start of the study.

An AE does not include:

- Medical or surgical procedure (e.g., surgery, endoscopy, tooth extraction, transfusion); the condition that leads to the procedure is an AE.
- Pre-existing diseases or conditions present or detected at the start of the study that do not worsen.
- Situations where an untoward medical occurrence has not occurred (e.g., hospitalization for cosmetic elective surgery, social and/or convenience admissions).
- Overdose of either study drug or concurrent medication without any signs or symptoms.

- Hospitalization for elective treatment of a pre-existing condition that did not worsen during the study is not considered an AE.

7.2. Definition of an Adverse Reaction

An adverse reaction means any AE caused by an investigational product. Adverse reactions are a subset of all suspected adverse reactions where there is reason to conclude that the investigational product caused the event.

7.3. Definition of a Suspected Adverse Reaction

A suspected adverse reaction is any adverse event for which there is a reasonable possibility that the investigational product caused the adverse event. “Reasonable possibility” means there is evidence to suggest a causal relationship between the investigational product and the AE. A suspected adverse reaction implies a lesser degree of certainty about causality than adverse reaction.

7.4. Definition of an Unexpected Adverse Event

An adverse event or Suspected Adverse Reaction is considered “unexpected” if it is not listed in the investigator brochure, product labeling or is not listed at the specificity or severity that has been observed.

7.5. Definition of a Serious Adverse Event

An SAE is any AE occurring at any dose that results in any of the following outcomes:

- a. Death
- b. A life-threatening AE
 - NOTE: Life-threatening means that the Subject was, in the view of the Investigator, at immediate risk of death from the event as it occurred. This definition does not include an event that, had it occurred in a more severe form, might have caused death.
- c. Inpatient hospitalization or prolongation of existing hospitalization
 - NOTE: Complications that occur during hospitalization are AEs. If a complication prolongs hospitalization, the event is an SAE.
 - NOTE: “Inpatient” hospitalization means the Subject has been formally admitted to a hospital for medical reasons. This may or may not be overnight. It does not include presentation at a “casualty” or emergency department.
- d. A disability/incapacity
 - NOTE: The term disability means a substantial disruption of a person’s ability to conduct normal life functions. This definition is not intended to include experiences of relatively minor medical significance such as uncomplicated headache, nausea, vomiting, diarrhea, influenza, accidental trauma (i.e., sprained ankle) that may interfere or prevent everyday life functions but do not constitute a substantial disruption.
- e. A congenital anomaly in the offspring of a Subject who received drug
- f. Important medical events that may not result in death, be life-threatening, or require hospitalization may be considered an SAE when, based upon appropriate medical judgment, they may jeopardize the Subject and may require medical or surgical intervention to prevent one of the outcomes listed in this definition. Examples of such medical events include allergic bronchospasm requiring intensive treatment in an emergency department or at home, blood dyscrasias or convulsions that do not result in Subject hospitalization, or the development of drug dependency or drug abuse.
 - NOTE: Medical and scientific judgment should be used in deciding whether prompt reporting is appropriate in this situation.

7.6. Severity of Adverse Events and Serious Adverse Events

Mild	- The symptom is barely noticeable to the Subject and does not influence performance or functioning.
Moderate	- The symptom is of sufficient severity to make the Subject uncomfortable, and performance of daily activities is influenced. Treatment for the symptom may be needed.
Severe	- The symptom causes severe discomfort. Treatment for the symptom may be necessary.

The severity (mild, moderate, or severe) of each AE or SAE must be assessed by the Investigator or designee.

7.7. Outcome of Adverse Events and Serious Adverse Events

Not Recovered / Not Resolved	- One of the possible results of an AE outcome that indicates that the event has not improved or the patient recuperated.
Recovered / Resolved	- One of the possible results of an AE outcome that indicates that the event has improved or patient recuperated.
Recovered / Resolved with Sequelae	- One of the possible results of an AE outcome where the subject recuperated but retained pathological conditions resulting from the prior disease or injury.
Recovering / Resolving	- One of the possible results of an AE outcome that indicates that the event is improving.
Unknown	- Not known, not observed, not recorded, or refused.
Fatal	- The termination of life as a result of an AE.

7.8. Assessment of Relatedness to Study Product

The Investigator will assess each AE and SAE for causality based on their best medical judgment, the observed symptoms associated with the event, and the available information on investigational product. The relatedness guidance provided below can be used to assist in determining the relationship of the IP to the AE or SAE. However, it is ultimately the investigator's responsibility to determine the relationship based on their best medical judgment, knowledge, and experience.

Not Related	- Based upon available information regarding subject history, disease process, relationship of AE to dosing and drug pharmacology, there is no reasonable relationship between the investigational product and the AE.
Possibly Related	- Relationship exists between the AE and IP, when the AE follows a reasonable sequence from the time of the investigational product administration, but could also have been produced by the subject's clinical state or by other drugs administered to the subject.
Probably Related	- Relationship exists between the AE and the investigational product when the AE follows a reasonable sequence from the time of investigational product administration, follows a known response pattern of the drug class, is confirmed by improvement on stopping the investigational product and the investigational product is the most likely of all causes.

Definitely Related - Relationship exists between the AE and the investigational product when the AE follows a reasonable sequence from the time of the investigational product administration, follows a known response pattern of the drug class, is confirmed by improvement on stopping the investigational product and no other reasonable cause exists.

7.9. Method, Frequency, and Time Period for Detecting Adverse Events and Serious Adverse Events

AEs and SAEs will be assessed in the frequency and manner as described in Section 6.2 of this protocol.

7.10. Reporting Serious Adverse Events

7.10.1. Timeframes for Reporting Serious Adverse Events

Prompt notification of the sponsor regarding SAEs is essential so that ethical and regulatory responsibilities and legal obligations can be satisfied. The Investigator must report SAEs according to the following time frames:

- Initial notification of all SAEs based on the available information must be provided to the sponsor or designee within 24 hours of the investigational site learning of the event. (Initial notification within 24 hours of Death and life-threatening events is extremely important).
- Follow-up information when available must be sent to the sponsor or designee within 48 hours of receipt of the information by the investigational site.

7.10.2. Serious Adverse Event Information to Report

At a minimum, SAE reports must contain the Subject ID, the serious adverse event term, onset date, relationship to study product, and a brief narrative of the event. Please note that relationship to study product and causality is very important and must be included in the initial report as it may impact expedited regulatory reporting requirements for the event.

There may be instances when copies of medical records for certain cases are requested. However, it is not acceptable for the Investigator to send photocopies of the Subject's medical records in lieu of completion of the appropriate AE and SAE pages. If medical records are submitted, all Subject personal identifiers must be completely redacted prior to submission.

7.10.3. Other Assessments as Adverse Events and Serious Adverse Events

The Investigator should exercise his or her medical and scientific judgment in deciding whether an abnormal laboratory finding or other abnormal assessment is clinically significant.

Abnormal laboratory findings (e.g., clinical chemistry, hematology, and urinalysis) or other abnormal assessments (e.g., electrocardiogram, vital signs) that are judged by the Investigator as clinically significant must be recorded as AEs or SAEs if they meet the definition of an adverse event. Clinically significant abnormal laboratory findings or other abnormal assessments that are detected after study product administration or that are present before study product administration but worsen after study product administration should be assessed for AE criteria.

7.10.4. Documenting Adverse Events and Serious Adverse Events

All AEs, including SAEs that occur after dosing of study product must be documented in the Subject's medical records and on the CRF. The Investigator should attempt to establish a diagnosis of the event based on signs,

symptoms, and/or other clinical information. In such cases, the diagnosis should be documented as the AE and/or SAE term.

7.10.5. Regulatory and Ethics reporting requirement

The Investigator will comply with the applicable local regulatory requirements related to the reporting of SAEs to the Institutional Review Board.

7.10.6. Follow-up of Adverse Events and Serious Adverse Events

All AEs and SAEs documented at a previous visit/contact that are designated as ongoing will be reviewed at subsequent visits/contacts. AEs and SAEs will be followed until the last study visit unless the nature of the AE or SAE requires continued monitoring. If a Subject dies during participation in the study or during a recognized follow-up period, a copy of any post-mortem findings, including histopathology, should be obtained, if available, and forwarded to scPharmaceuticals. New or updated information will be recorded on the originally completed SAE Report Form with all changes electronically signed/dated by the Investigator or designee.

8. STATISTICS

8.1. Determination of Sample Size

Based on an average hospital cost of a patient hospitalized for \leq 72 hours with a primary diagnosis of HF (Diagnosis Related Group Code 291, 292 and 293) of \$8,600 (standard deviation: \$3,045), 68 patients (34 in each group) are required to have an 80% chance of detecting a decrease in hospital costs to \$6,500 at a significance level of 5%. The target sample size of the Furoscix cohort will initially be N=34 subjects.

Given the anticipated overdispersion of the primary outcome (i.e., difference in total HF-attributable direct medical costs), we will employ adaptive trial design procedures for sample size re-estimation. This adaptive-total information criterion approach was taken due to the risk of incorrectly estimating the sample size due to misspecification of the cost outcome parameters. By using the adaptive sample size design, which includes no penalty for repeated interim analysis, the final sample size will be sufficient to provide adequate power to test the stated hypothesis.

This will include re-assessment of the sample size at N=34 in the Furoscix cohort by using a group sequential design and testing to allow for stopping. It is not expected that the sample size for the Furoscix Infusor arm would exceed N=75, but the maximum value cannot be definitively stated until the analysis at N=34 is completed.

We will explore ratios ranging from 1:1 to 4:1 for the number of historical controls to be matched to Furoscix-treated patients using methods reported by Millar and Pasta 2010. The simulations will be used to find the matching ratio at which the level of precision is optimized without biasing the variance of the outcome measure. Additional methodological details are described in the prespecified statistical analysis plan.

The methodology by which the sample size will be re-estimated and stopping rules will be implemented will be detailed in the statistical analysis plan.

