3.3.5. Trial Design

A group sequential design is being employed to allow for stopping due to futility or efficacy. This design includes the following general steps (cite SAS manual for group sequential designs):

1. Specify the statistical details of the design, including the null and alternative hypotheses (null hypothesis being that there is no difference in 30-day HF-related direct medical costs between the Furoscix Infusor and historical control arms), a test statistic for the hypothesis test, the Type I and II error probabilities, a stopping criterion, the total number of stages, and the relative information level at each stage.
2. Compute the boundary values for the trial based on the specifications in Step 1 and compute the sample size required at each stage for the specified hypothesis test.
3. At each stage, collect additional data with the required sample sizes. This includes the data collected at the current stage in addition to the data collected at previous stages.
4. At each stage, analyze the available data and compute the test statistic.
5. At each stage, compare the test statistic with the corresponding boundary values. The trial will stop to reject or accept the hypothesis, or it will continue to the next stage.
6. Once the trial stops, parameter estimates, confidence limits for the parameter, and a p-value for the hypothesis test are computed.

Below is a depiction of a hypothetical 4-stage design with two-sided testing.

Figure 1. Boundaries for Two-Sided Group Sequential Test

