The four stages of the hypothetical trial presented in the preceding figure are indicated by vertical lines labeled 1, 2, 3, and 4. With early stopping to reject the null hypothesis, the lower rejection boundary is constructed by connecting the lower critical values for the stages. Similarly, the upper rejection boundary is constructed by connecting the upper critical values for the stages. The horizontal axis indicates the sample size for the group sequential trial, and the vertical axis indicates the values of the test statistic on the standardized Z scale. At each interim stage, if the test statistic falls into a rejection region the trial stops and the null hypothesis is rejected. Otherwise, the trial continues to the next stage. At the final stage the null hypothesis is rejected if Z falls into the rejection region. Otherwise, the null hypothesis is not rejected. In the figure, the test statistic falls into the rejection region in stage 3 and the null hypothesis is rejected.

An important concern with group sequential designs is correcting for multiplicity caused by conducting multiple, sequential correlated statistical tests thereby increasing the probability of Type 1 error. To correct for this issue one must preemptively define local significance levels for each statistical test and define the stopping boundaries. Herein, we will employ the O'Brien and Fleming error spending function to distribute the overall Type 1 error rate across the interim and final analyses. Because the O'Brien and Fleming approach includes an increase in the local significance level with each subsequent analysis (i.e., with each stage) it is considered among the more conservative approaches.

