3.5.4. Step 3: Compute Boundary Values for Primary Outcome

Boundary values for the primary outcome will be derived via the SEQDESIGN (REF SAS SEQDESIGN) procedure in SAS; specifically using a two-sided O’Brien Fleming design which has conservative stopping boundary values at early stages, and boundary values at the final stage that are close to the fixed-sample design. This produces a conservative design because compared to other approaches, the O’Brien-Fleming approach makes it more difficult to reject the null hypothesis in early stages than in later stages (null hypothesis being that there is no difference in 30-day HF-related direct medical costs between the Furoscix Infusor and historical control arms).

Assume that the total 30-day HF-related direct medical costs are normally distributed with means μ_e and μ_c for individuals in the Furoscix Infusor and historical control groups, respectively. The null hypothesis of no effect for the Furoscix Infusor is $H_0 : \theta = 0$, where $\theta = \mu_e - \mu_c$

The specific procedure for determining the boundary values for the primary outcome are specified elsewhere (REF SAS SEQDESIGN). Utilizing this procedure requires that we prespecify the meaningful difference between groups and the standard deviation thereof in order to achieve the specified power. The boundary values will be estimated based on a difference of \$2,100 (based an average hospital cost of a patient hospitalized for ≤ 72 hours with a primary diagnosis of HF (Diagnosis Related Group Code 291, 292 and 293) of \$8,600 (standard deviation: \$3,045), 68 patients (34 in each group) are required to have an 80% chance of detecting a decrease in hospital costs to \$6,500 at a significance level of 5%).

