3.5.5. Step 4: Interim and Final Analysis with Propensity Match

Interim analyses to determine whether efficacy or futility has been reached will be conducted in a prespecified manner at N=10 and N=34 in the evaluable population. Additional interim analyses may be conducted as needed. Note that the enrollment for the prospective arm will continue as the interim analysis is carried out up to N=34, at which point re-assessment of sample size will be conducted.

For the interim analyses, the comparators will be historical controls drawn from the aforementioned candidate pool using a 1:1 to 4:1 propensity score matched approach. The propensity score matching process will be conducted via a caliper-based mechanism that allows for an iterative matching approach that will maximize the efficiency of the match protocol using methods reported by Millar and Pasta 2010.

The primary final analysis will include a 1:1 to 4:1 propensity match using the identical algorithm produced in the last interim analysis. Additional final analyses will explore the impact of increasing the ratio of cases to controls up to a 1:10 match. Note that the aforementioned matching method will be applied so that no Furoscix subjects will be dropped from the analysis due to the lack of a suitable match or matches.

The propensity scores (1 for each case and control) will be generated with the SAS PROC LOGISTIC function to produce a multivariate logistic regression. The propensity score is the predicted probability of receiving the Furoscix Infusor treatment. Both automatic stepwise and manual variable selection will be evaluated.

Criteria for propensity score matching are listed below:

- In addition to requiring that the absolute difference between the treatment arm propensity score and the control patient's propensity score be no larger than 0.01, exact sex, the absolute difference in age could be no larger than 5 years, and time between time zero visits could be no more than 730 days (or 1095 days). These key measure requirements reduced the data set substantially to a data set of potential matches.

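### The maximum N, number of stages and re-estimation rule are not fixed before the comparative N=34 look, so the two-sided 5% for the primary test is not assured

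*Protocol*

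**What the plan says.** SAP 3.3.3 sets the primary test at two-sided 0.05. SAP 3.3.5 states: "A group sequential design is being employed to allow for stopping due to futility or efficacy". It relies on an O'Brien-Fleming "error spending function to distribute the overall Type 1 error rate across the interim and final analyses", and step 1 of its design list names "a stopping criterion, the total number of stages, and the relative information level at each stage" among the items to be specified. No values follow there or in SAP 3.5.4, which sends the boundary calculation to SEQDESIGN with a difference of $2,100, an SD of $3,045 and 80% power.

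SAP 3.5.5 says that interim analyses for efficacy or futility "will be conducted in a prespecified manner at N=10 and N=34 in the evaluable population", and then: "Additional interim analyses may be conducted as needed". The N=34 analysis is therefore a comparative look as well as the point of sample size re-assessment.

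On the maximum, the Protocol synopsis, Protocol 5.10, Protocol 8.1 and SAP 3.5.2 all say that "the maximum value cannot be definitively stated until the analysis at N=34 is completed". N=75 appears only as a figure that is not expected to be exceeded.

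Four other places bear on the point:

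- Protocol 8.1 describes the method as based on a total-information criterion, and leaves the re-estimation and stopping details to the SAP. The SAP contains no re-estimation formula.
- Protocol 5.10 stops the study at a fixed confidence interval width. No width is given, and the SAP does not mention the rule.
- Protocol 8.1 also says that repeated interim analysis carries no penalty.
- Protocol 9.2.2 exempts adaptive sample size increases from the amendment rule.

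**The concern.** Error spending allocates alpha by information fraction, so each boundary needs a denominator: the maximum information. Without one, the boundary at N=34 is undefined. If the maximum is then set after the N=34 cost difference has been seen, the same data could be a rejection or a continuation depending on a number chosen afterwards.

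SEQTEST's adjustment to observed information, described in SAP 3.5.5, does not repair this. It protects alpha when the maximum is fixed, or is changed without using the treatment difference, and when look times do not depend on results. The plan states neither condition. At stake is whether a primary result reported at two-sided 5% was tested at that level.

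**Working it through.** **Inputs.** Two-sided alpha 0.05 (SAP 3.3.3). Difference $2,100, SD $3,045, 34 per group, 80% power (Protocol 8.1, SAP 3.5.4). Looks at N=10 and N=34 (SAP 3.5.5). Expected ceiling 75 (Protocol 8.1, SAP 3.5.2).

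**Assumptions.** Normal test statistic, information proportional to N, and, for error rates, null true and no futility stop. Skewed costs are not modelled.

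**1. The plan's own figure.** n per group = 2 × (1.960 + 0.842)² × (3,045/2,100)² = 33.0 by the normal formula. A two-sample t-test at 34 per group has power 80.0%. The stated 34 is reproduced, as a fixed-sample figure at 1:1.

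**2. The N=34 boundary.** Two-sided Lan-DeMets O'Brien-Fleming spending is α(t) = 4 × [1 − Φ(2.2414/√t)], with t = 34/maximum. The N=10 look spends almost nothing (1.7e-9 if the maximum is 75), so the N=34 bound is the |Z| whose two-sided p equals α(t).

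| Maximum N | t | α(t) | Critical \|Z\| at N=34 |
|---|---|---|---|
| 34 | 1.000 | 0.0500 | 1.96 |
| 50 | 0.680 | 0.0131 | 2.48 |
| 75 | 0.453 | 0.0017 | 3.13 |
| 100 | 0.340 | 0.0002 | 3.67 |

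**3. Maximum fixed at 75.** Recursive integration over N=10/34/75 gives |Z| of 6.03/3.13/1.965 and total type I error 5.0%. The classical O'Brien-Fleming design gives 5.40/2.93/1.972.

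**4. Final N chosen from the N=34 result.** Hold 3.13 at N=34. For each possible final N, solve the final bound b so that total alpha would be 0.05 if that N had been fixed in advance (b = 1.960 at N=35, 1.965 at N=75). Given z at N=34, the chance of rejecting under the null is

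CP(z, N) = 1 − Φ[(b√N − z√34)/√(N−34)] + Φ[(−b√N − z√34)/√(N−34)].

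For each |z| < 3.13 take the N in the allowed range that maximises CP, integrate over the standard normal density, and add the 0.0017 already spent.

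| Allowed final N | Worst-case type I error |
|---|---|
| 35–75 | 8.1% |
| 40–75 | 7.0% |
| 45–75 | 6.4% |
| 50–75 | 6.0% |
| 60–75 | 5.5% |
| 35–150 | 9.1% |

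A less extreme rule picks the N that gives 80% conditional power at the observed trend. It gives 7.4% if trials that cannot reach 80% run to 75, and 4.6% if they end at N=35. If the N=34 bound were itself also set after the result, the worst case with N up to 75 would be 8.6%.

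**5. Added looks alone.** With the maximum fixed at 75, one extra look between N=36 and N=74, timed from the N=34 result, raises the worst case only to 5.2%. The open maximum is the larger problem.

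**6. Cost of fixing N=75.** At the design effect the expected Z at N=34, 1:1, is 2,100/[3,045 × √(2/34)] = 2,100/738.5 = 2.84. The chance of crossing 3.13 is Φ(2.84 − 3.13) = 0.387, so about 61% of trials would continue.

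**The case against.** The strongest reply is that the Protocol intends information-based monitoring. Its total-information criterion, its stated worry about misjudged cost parameters and its fixed interval width all point that way. In such a design the information is fixed, N follows the variance, and not knowing the final N until N=34 is normal. This stands in part: an unknown final N is not itself the fault, and under such a rule inflation would be small. But no information target, interval width or rule is written, and nothing bars use of the cost difference. Intent does not supply a boundary.

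The SAP's administrative section also allows revision with approvals, so the maximum could be added later. It does not require that before the N=34 look.

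Three stronger readings go beyond the documents:

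- A reader might infer from the no-penalty clause in Protocol 8.1 that each look is tested at an unadjusted 5%. SAP 3.3.5 and 3.5.4 exclude that, and the clause sits in a sentence about power. It is a wording conflict.
- A reader might take 8.1% as the trial's error rate. It needs a final N picked to maximise rejection, with stopping allowed one subject after the look and a cap of 75 that the text does not impose. No document describes such a choice.
- A reader might infer that looks taken as needed break error spending by themselves. Step 5 of the working shows they add little once the maximum is fixed.

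**Conclusion.** The concern holds as a loss of assurance. The N=34 critical value, and hence the two-sided 5% level, cannot be derived from the plan. Under assumed result-driven choices of final N, type I error runs from about 5% to 8%: 5.5% for final N 60–75, 6.0% for 50–75, and 8.1% only if the trial may end at N=35. It is about 9% if N may reach 150. These figures hold the N=34 bound at 3.13. With the maximum fixed in advance the error is 5.0%.

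All of this assumes a normal statistic with information proportional to N. The exact 5.0% could also be disturbed by skewed costs, rematching at each look and updating of the control pool, which are not modelled here.

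**What to change.** In SAP 3.5.4 and 3.5.5, before any further comparative look:

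1. **Fix the maximum**, in one of two ways.
   - *N=75*, the documents' own expected ceiling, with Lan-DeMets |Z| of 6.03/3.13/1.965 at N=10/34/75 and type I error 5.0%.
   - *A stated information target*, with N re-estimated from the variance only, without the cost difference, and capped at 75. An example is an SE of $739 for the matched difference (3,045 × √(2/34)). In simulation (normal, uncorrelated matched costs, paired t, 1:1) type I error is about 5.1–5.5%. Power is 83%, 80%, 76% and 71% at SDs of $3,045, $3,800, $4,522 and $5,000. The SAP should state both the slight excess over 5% and that the cap limits power at larger SDs.
2. **Replace the sentence** "Additional interim analyses may be conducted as needed" with a rule that added looks are timed without reference to comparative results and spend from the same function.
3. **Align the Protocol.** In 8.1, refer to the SAP's error spending in place of the no-penalty clause. In 5.10, express the interval width as the same target (SE $739 is a 95% half-width of 1.96 × 739, about $1,450) or remove the rule.

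Supporting detail: name the O'Brien-Fleming variant, since 3.3.5 speaks of a spending function and 3.5.4 of an O'Brien "Fleming design which has conservative stopping boundary values at early stages". State the matching ratio that the information assumes. State the futility boundary and whether it is binding, because the worked example in 3.3.5 has rejection regions only ("Otherwise, the trial continues to the next stage"). A particular futility rule is optional.

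The change is wording in both documents. Its price under N=75 is that an early win at N=34 needs p of about 0.002, and about 61% of trials at the design effect (1:1) would run past N=34.
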